10.4 Analyses by Dose

Given that TNX-102 SL is generally well tolerated, it is unlikely that a large number of subjects will have a dose reduction to one tablet and hence it is nearly certain that an insufficient number will have such a reduction so as to allow the multiple imputation algorithm return stable results taking dose into account. If more than 10 subjects in the active arm have a dose reduction at any point in the study, summary statistics on observed values for the primary and key secondary outcomes will be reported for placebo and each dose, with active treatment subjects grouped by whether they had a PI-directed dose reduction at any time point, regardless of the dose they were on at a particular time point. Placebo subjects that had a “dose reduction” will not be grouped separately.

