visit in order to collect greater safety data than the telephone visits allow. The Screening phase will be followed by the Baseline/Randomization Visit (Visit 2, Day 1), and 4 treatment visits at Weeks 2, 6, 10, and 14 (or Early Termination). The total duration of the study, including Screening, will be approximately 15-19 weeks. The maximum treatment duration will be 14 weeks.

Eligible patients who provide written informed consent will have study assessments performed at Screening and will stop all excluded medications during the washout period through the Week 14 visit (Visit 6). Patients will record their average pain intensity for the previous 24 hours in the evening every day from Visit 1 through Visit 6 on a diary system. After recording Baseline Diary scores for at least 7 days, patients will return to the investigative site for Baseline assessments and randomization (Day 1), where they will be randomly assigned to receive TNX-102 SL or matching placebo sublingual tablets in a 1:1 ratio.

Patients will take the study drug sublingually daily at bedtime, starting on the day that they are randomized (Day 1), for 14 weeks. For the first two weeks of treatment, patients will start on TNX-102 SL 2.8 mg (1 tablet) or placebo. Upon return to the site¹ for the Week 2 visit (Visit 3), all patients will have the dose increased to TNX-102 SL 5.6 mg (2 x 2.8 mg tablets) or two placebo tablets. Patients will return to the site¹ for assessment of efficacy and safety, as well as dose tolerability, at Weeks 6, 10, and 14 (or Early Termination).

In scenarios in which TNX-102 SL 5.6 mg, or 2 placebo tablets, is considered intolerable and would otherwise lead to study discontinuation, the Investigator may lower the dose back to 1 tablet every night (TNX-102 SL 2.8 mg or one placebo tablet). Re-challenge with 2 tablets TNX-102 SL 2.8 mg (5.6 mg dose)/placebo may be attempted at a later date if/when it is deemed clinically warranted by the Investigator, or the patient may remain on the lower dose for the remainder of the study.

Patients who wish to withdraw from the study may do so at any time.

Patients will be trained on use of the diary system at the Screening visit. Each evening, when the patient utilizes the diary, the system will prompt the patient regarding daily average pain intensity, sleep quality from the previous night, and study drug dosing the previous night (post-randomization).

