Eligible subjects who provide written informed consent will have study assessments performed at Screening and will stop all excluded medications during the washout period through the Week 14 visit (Visit 6). Subjects will record their average pain intensity for the previous 24 hours in the evening every day from Visit 1 through Visit 6 on an electronic diary system. After recording Baseline Diary scores for at least 7 days, subjects will return to the investigative site for Baseline assessments and randomization (Day 1), where they will be randomly assigned to receive TNX-102 SL or matching placebo sublingual tablets in a 1:1 ratio. Subjects will take the study drug sublingually daily at bedtime, starting on the day that they are randomized (Day 1), for 14 weeks. For the first two weeks of treatment, subjects will start on TNX-102 SL 2.8 mg (1 tablet) or placebo. At the Week 2 visit (Visit 3), all subjects will have the dose increased to TNX-102 SL 5.6 mg (2 x 2.8 mg tablets) or 2 placebo tablets. Subjects will return to the site for assessment of efficacy and safety, as well as dose tolerability, at Weeks 6, 10, and 14 (or early termination), unless a telephone visit is conducted, in which case certain assessments that cannot be done over the phone (e.g. vitals and oral cavity exam) are allowed to be omitted, which is specifically stated in the protocol. In scenarios in which 5.6 mg dose is considered intolerable and would otherwise lead to study discontinuation, the Investigator may lower the dose back to TNX-102 SL 2.8 mg or one placebo per day. Re-challenge with TNX-102 SL 5.6 mg or 2 placebo tablets may be attempted at a later date if/when it is deemed clinically warranted by the Investigator, or the subject may remain on the lower 2.8 mg dose for the remainder of the study.

Subjects who wish to withdraw from the study may do so at any time.

Subjects will be trained on use of the diary system at the Screening visit. Each evening, when the subject utilizes the diary, the system will prompt the subject regarding daily average pain

intensity and sleep quality from the previous night, and, starting Day 2 post-randomization, regarding study drug dosing the previous night.

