9. STUDY SUBJECTS AND DEMOGRAPHICS

9.1 Disposition of Subjects and Withdrawals

The numbers and percentage of subjects screened, randomized, completing the study, and withdrawing from the study, along with reasons for withdrawal, will be tabulated overall and by treatment group. The number and percentage of subjects in each analysis population will be reported. Additionally, the number and percentage of subjects that have an investigator-directed dose reduction from two tablets per day to one tablet per day will be summarized. The disposition and withdrawal summaries will be based on all subjects who have data entered into the database.

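### The by-dose summary splits active patients by ever having a dose reduction, pools placebo patients who had the same reduction, and labels the groups as doses

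*SAP*

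**What the plan says.** SAP 10.4 sets a trigger: "If more than 10 subjects in the active arm have a dose reduction at any point in the study". Once it is met, the section promises that "summary statistics on observed values for the primary and key secondary outcomes will be reported for placebo and each dose". The two active groups are then defined by dosing history and not by current dose: "with active treatment subjects grouped by whether they had a PI-directed dose reduction at any time point, regardless of the dose they were on". The section closes by saying that placebo patients who had a reduction "will not be grouped separately".

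A reduction is open to both arms. SAP 4 allows it when the higher dose "is considered intolerable and would otherwise lead to study discontinuation". In that situation, it says, "the Investigator may lower the dose back to TNX-102 SL 2.8 mg or one placebo per day". The Protocol synopsis gives the same rule. Re-challenge with two tablets is allowed, and Protocol 7.1 says a reduction may be temporary.

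The information is collected regardless of arm. Protocol 10.2 requires reductions to be documented in the CRF. SAP 9.1 adds, under disposition, that "subjects that have an investigator-directed dose reduction from two tablets per day to one tablet per day will be summarized", and SAP 12.3 tabulates the week of reduction.

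SAP 8.1 mentions the same kind of summary with the same trigger, but there it is optional. In 10.4 it is mandatory once triggered.

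**The concern.** The grouping variable arises after randomisation and selects patients on tolerability. Applied to the active arm only, it leaves a never-reduced active column without its intolerant patients, set beside a placebo column that still contains them. The reduced active column holds only such patients and is set beside all of placebo. Neither comparison is like with like.

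The per-dose label adds to the problem, because the columns do not hold outcomes on a given dose.

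What is at stake is interpretation. SAP 2 allows planned analyses into study reports, regulatory submissions and manuscripts. A table of the primary and key secondary outcomes arranged by dose invites a dose-response reading, and the layout omits the placebo split that would help a reader judge how much of any pattern is selection.

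**Working it through.** **Labels (no assumptions needed).** A patient first reduced at Week 12 appears in the reduced column for Weeks 3 to 11, when two tablets were scheduled. A patient who is re-challenged stays in that column afterwards. Every active patient is scheduled for one tablet on Days 1 to 14 (SAP 4.2), so Weeks 1 and 2 of the never-reduced column are not 5.6 mg either.

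**Inputs.**
- Arm size: 235 per arm (SAP 6); 2 × 235 = 470, the planned total.
- Trigger: more than 10 active reducers (SAP 10.4), so at least 11/235 = 4.7%.
- p, the share reducing: assumed, 4.7% to 20%. The documents give no rate; Protocol 5.4 expects reductions to be rare.
- d, the mean change in reducers minus that in non-reducers: assumed, 0 to 1.5 NRS points. Neither its size nor its sign is given.

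The plan states no figure for this summary, so there is none to reproduce.

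**Formula.** Let N and R be the mean changes in never-reduced and reduced active patients. The active-arm mean is M = (1 − p)N + pR, with R − N = d. With no drug effect the pooled placebo mean is also M in expectation. Hence, against pooled placebo:
- never-reduced active: N − M = −p × d
- reduced active: R − M = (1 − p) × d

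Negative values mean greater improvement.

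| p | d | Never reduced vs placebo | Reduced vs placebo | Never reduced minus reduced |
|---|---|---|---|---|
| any | 0 | 0 | 0 | 0 |
| 4.7% | 0.5 | −0.02 | +0.48 | −0.5 |
| 4.7% | 1.0 | −0.05 | +0.95 | −1.0 |
| 4.7% | 1.5 | −0.07 | +1.43 | −1.5 |
| 10% | 1.0 | −0.10 | +0.90 | −1.0 |
| 20% | 1.0 | −0.20 | +0.80 | −1.0 |
| 20% | 1.5 | −0.30 | +1.20 | −1.5 |

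A simulation of 20,000 trials with 235 per arm, an assumed SD of 2.0, p = 11/235 and d = 1 gave −0.048 and +0.946, in agreement.

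**Where the distortion falls.** Almost all of it is in the reduced column. The gap between the two active columns is d in absolute size, however placebo is shown.

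**Precision.** With 11 reducers and an assumed SD of 1.8 to 2.3, the standard error of reduced active against placebo is SD × √(1/11 + 1/235) = 0.56 to 0.71.

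**Effect of splitting placebo.** If p and d are the same in both arms, both matched contrasts are zero. If they differ, they need not be. Suppose no drug effect on pain, active p = 10% and d = 0.5, placebo p = 2% and d = 2 (all assumed). Active reducers sit 0.90 × 0.5 = +0.45 from the common mean and placebo reducers 0.98 × 2 = +1.96. The matched contrast is 0.45 − 1.96 = −1.51, which is larger in size than the +0.45 against pooled placebo.

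**The case against.** The strongest case on the other side is that little depends on this table.
- It is produced only after more than 10 active reductions, which both documents regard as unlikely.
- It consists of summary statistics on observed values, with no test, model or imputation.
- Efficacy is analysed by randomised arm (SAP 7), reducers stay in their arm (SAP 8.1), and anything outside the testing hierarchy is descriptive (SAP 8.1.1.2).
- The sentence with the per-dose label also states the grouping convention, so a careful reader is told what the columns contain.
- The contrast between the active columns comes from splitting active, not from pooling placebo.
- Drug-intolerant reducers and placebo reducers may be different kinds of patient, so a placebo split does not restore randomisation.

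All of this stands, and it limits the severity. It does not justify the asymmetry. The reason SAP 10.4 gives for not modelling by dose is unstable multiple imputation, which has no bearing on observed-value summaries. Stating the convention in the SAP does not correct a column label in the output.

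A reader might infer that the table is bound to show 5.6 mg beating placebo and 2.8 mg losing to it. The documents do not support that, because the pattern requires d above zero and they give neither its size nor its sign. It vanishes at d = 0 and reverses if reducers do better. A reader might also infer that splitting placebo yields a clean comparator with no artefact; the last calculation shows otherwise.

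**Conclusion.** The point holds as a minor defect of display. SAP 10.4 applies a tolerability-selected, post-randomisation split to one arm only and labels the result by dose although the groups are not defined by dose taken. The mislabelling and the asymmetry follow from the text alone.

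The numerical effect is conditional. At the trigger share and an assumed d of 1 point, the never-reduced column moves by about 0.05 points and the reduced column by about 0.95, the latter in a group small enough to be imprecise in any case. The primary and key secondary inference is untouched, and nothing here supports a claim that the trial's efficacy result is biased.

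**What to change.** In SAP 10.4:
- Delete the sentence that keeps placebo reducers pooled.
- Show active and placebo each as *ever reduced* and *never reduced*, using the same investigator-directed flag in both arms, with n in every cell.
- Remove the per-dose label.
- Add a footnote that the groups are not randomised, that active and placebo reducers may not be comparable, and that the display supports no dose-response conclusion.
- Reconcile SAP 8.1 (optional) with 10.4 (mandatory once triggered).

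The cost is one deleted sentence, one extra table column, a footnote and a change of wording. No new data are needed. The drawback is that the placebo-reduced cell may be very small or empty, since the trigger counts active patients only; showing n makes that visible.

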11. SAFETY AND TOLERABILITY ANALYSES

The safety analyses will be run on the Safety population. The analysis of safety in this study will include summaries of the following safety and tolerability data collected for each subject:

- Adverse Events
- Clinical Laboratory Investigations
- C-SSRS
- BDI-II
- Vital Signs
- Physical Examinations and examinations of the oral cavity

11.1 Adverse Events

All AEs, TEAEs, and SAEs will be coded using the MedDRA Dictionary Version 22.1.

The collection of adverse events will begin at the time the subject is consented and screened for the study. Treatment-emergent adverse events (TEAEs) are defined as either new onset AEs with an onset at the time of or following the start of treatment, as indicated by a “no” answer to “Did AE start prior to the first dose?”, or a recurrence of an AE (or medical history) present prior to randomization but increasing in severity, frequency or relationship at the time of or following the start of treatment.

An AE summary table will be presented for the following:

- All TEAEs
- TEAEs by severity
- TEAEs leading to study drug discontinuation
- TEAEs by relationship
- SAEs
- Oral cavity TEAEs
- Oral cavity TEAEs by severity

Summaries of incidence rates (frequencies and percentages), of individual AEs by MedDRA SOC and preferred term will be prepared. Such summaries will be displayed for all TEAEs, oral cavity TEAEs, TEAEs by maximum severity, TEAEs by strongest relationship to study drug and post-treatment AEs.

Each subject will be counted only once within each summation level (SOC; preferred term). If a subject experiences more than one TEAE within each summation level, the TEAE with the strongest relationship or the maximum severity, as appropriate, will be included in the summaries of relationship and severity.

In the AE data listings, all AEs will be displayed. AEs that occur prior to randomization will be considered pre-treatment AEs, and will be determined by a “yes” response to the CRF question, “Did the AE start prior to the first dose?” AEs that start on the date of randomization but have a “yes” response to this question will be categorized as pre-treatment AEs. TEAEs will be defined

from the date of randomization and a “no” response to the CRF question, “Did the AE start prior to the first dose?”

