5.4. Conclusion for Study Design

[REDACTED]

The present study is a Phase 3, randomized, double-blind, multicenter trial designed to evaluate the efficacy and safety of TNX-102 SL 5.6 mg (2 x 2.8 mg tablets) taken once daily at bedtime compared to placebo over 14 weeks in patients with fibromyalgia. Since fibromyalgia patients are often quite sensitive to medication side effects, the protocol includes a 2 week dose titration starting at 2.8 mg dose, followed by an increase to 5.6 mg from Day 15 through end of study. Additionally, to mitigate the potential for discontinuations due to tolerability at 5.6 mg in the FM population, the protocol includes a provision for the Investigator to reduce the dose back to one tablet daily at bedtime, either temporarily, or for the duration of the study, in order to prevent missing data due to AE-related discontinuations. Even so, the goal and design of the study is to always encourage the continued dosing with TNX-102 SL 5.6 mg nightly after the initial 2-week dose titration phase, and it is anticipated that dose lowering will only rarely be necessary in the study.

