10.2. Dosing Instructions

Patients will be instructed to take 1 tablet of randomly assigned study drug TNX-102 SL 2.8 mg or SL placebo tablet sublingually, under the tongue, each evening at bedtime starting at bedtime on Day 1 (Day of Visit 2) and continuing through Day 14. At the Week 2 visit, patients will be instructed to increase the dose to 2 tablets at bedtime, administered simultaneously and under the tongue beginning on Day 15 and continuing through the end of the study.

The study drug should be taken at bedtime after teeth brushing and other oral care has been completed. The mouth/sublingual area should be moist at the time of dosing, so the patient should drink a few sips of water prior to dosing, especially if prone to dry mouth. Patients will be instructed to place the one or two SL tablets under their tongue (if two, placed simultaneously under tongue) and keep them there until they have dissolved (approximately 90 seconds). They should not swallow, crush or chew the tablets. Patients should not eat or drink (or chew gum) for at least 15 minutes after dosing, and preferably not to drink any hot, cold or acidic beverage until

¹ All references to a site/study center visit for Weeks 2, 6, 10, and 14 include telephone visits for Weeks 2, 6, and 10, and home visits or telephone visit for Week 14/ET that are being allowed due to the circumstances of the COVID-19 pandemic.

morning. Patients also should not talk for at least 5 minutes after placing the study drug in the mouth (under the tongue). Patients will be reminded that only 2 (two) tablets are allowed per day. Note: In the event that the patient misses a dose, instruct the patient to continue dosing with two (2) tablets the next evening; i.e., they should not take more to make up for the missed dose.

If the patient reports intolerable side effects that are likely to result in premature discontinuation from the study, then the dose of study drug may be reduced to one tablet sublingually nightly. Any reduction in study drug dose must be carefully documented in the CRF. The goal is for the patient to be on a stable and final dose of study drug starting from the Week 2 visit, at the highest dose tolerated (preferably two TNX-102 SL tablets daily at bedtime).

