10.3. Dispensing Instructions

Each patient who has met the randomization criteria (Section 8.4) will be assigned a double-blind treatment bottle at Visit 2 via the Interactive Response Technology (IRT), with a unique, but otherwise random bottle number that is generated when the study coordinator successfully completes randomization procedures. Patients will take one sublingual tablet each evening before bedtime for the first 2 weeks.

Study treatments for the double-blind treatment phase are either:

Treatment A: 2 × TNX-102 SL 2.8 mg tablets (“TNX-102 SL”) to be taken sublingually (simultaneously) once daily at bedtime.

Treatment B: 2 × placebo tablet (“placebo”) to be taken sublingually (simultaneously) once daily at bedtime.

Beginning with the evening of the Week 2 Visit, patients will take 2 sublingual tablets each evening before bedtime, and will continue doing so throughout the course of the study. Only in the event of adverse events that might possibly lead to discontinuation can the patient reduce the dose to 1 tablet per evening, with approval of the Principal Investigator.

In the event of loss of a study drug bottle, a new bottle will be provided by the IRT when appropriately requested by the site and/or the sponsor or designee.

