11.1.1 Adverse Events Leading to Discontinuation of Study Drug

A summary of incidence rates (frequencies and percentages) of TEAEs leading to discontinuation of study drug by treatment group, SOC, and preferred term will be prepared for the Safety population.

A data listing of AEs leading to discontinuation of study drug will also be provided, displaying details of the event(s) captured on the CRF.

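### No planned table shows which adverse events led to dose reduction, so the discontinuation table read alone can understate AE-limited intolerance of 5.6 mg

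*SAP*

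**What the plan says.** **Purpose of dose reduction.** Protocol 5.4 explains that stepping back to one tablet is provided "in order to prevent missing data due to AE-related discontinuations". Protocol 10.3 restricts its use: "Only in the event of adverse events that might possibly lead to discontinuation can the patient reduce the dose to 1 tablet per evening". SAP 4 and 4.4 describe the same provision. Protocol 10.2 adds: "Any reduction in study drug dose must be carefully documented in the CRF".

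**AE tables.** SAP 11.1 and Protocol 13.5 both list a summary of "TEAEs leading to study drug discontinuation". SAP 11.1.1 gives it in detail: a summary of "TEAEs leading to discontinuation of study drug by treatment group, SOC, and preferred term will be prepared for the Safety population". Neither document lists a counterpart for TEAEs leading to dose reduction.

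**Where reductions do appear.**
- SAP 9.1 (disposition): number and percentage of patients with an investigator-directed reduction.
- SAP 12.3 (exposure): number and percentage dropping to one tablet, the week of the drop, and days on each dose.
- SAP 10.4: if more than 10 active-arm patients reduce, "summary statistics on observed values for the primary and key secondary outcomes will be reported for placebo and each dose". This covers efficacy outcomes only, and placebo patients who reduced are not grouped separately.
- SAP 8.1: reduced patients otherwise stay within their treatment group and are not reported separately unless noted.

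**The concern.** The secondary objective is the safety of the 5.6 mg dose. In most trials, the proportion of patients stopping drug for an AE is a natural summary of intolerance. Here the protocol deliberately provides a second route. A patient who cannot tolerate two tablets may step down to one and stay in the trial, and that patient does not enter the discontinuation table.

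The two outcomes are linked by design, but the AE tables identify only one of them. A reader of the study report could not tell from any planned table which events limited the dose, or how many distinct patients had 5.6 mg reduced or stopped for an AE. If intolerance is drug-related, more patients would be missing from the active arm than from placebo, so the between-arm contrast in that table would also look smaller than it should.

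**Working it through.** The plan states no figure on this point, so there is none to reproduce. The check has two parts.

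**1. What each planned output can show**

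| Output | Counts reduced patients? | Names the AE that led to reduction? | Shows overlap with AE discontinuation? |
|---|---|---|---|
| All-TEAE, severity, relationship and oral cavity tables (SAP 11.1) | No; the events are included but not identified | No | No |
| TEAEs leading to discontinuation (SAP 11.1, 11.1.1) | Only if they later stop for an AE | No | No |
| Disposition (SAP 9.1) | Yes | No | No |
| Exposure (SAP 12.3) | Yes, with week | No | No |
| By-dose summaries (SAP 10.4) | Active arm only, if more than 10 reduce | No | No |

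The counts in SAP 9.1 and 12.3 cannot simply be added to the AE discontinuations, because a patient may reduce and later stop.

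**2. Size of the gap**

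Inputs: n = 235 per arm (SAP 6), taking every randomised patient as dosed. D = patients stopping for an AE. R = patients reducing for an AE. O = patients who do both. D, R and O are assumptions, because the documents give no rates.

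- Discontinuation table: D/n
- Either outcome, each patient once: (D + R − O)/n
- Gap: (R − O)/n

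With no overlap (O = 0), for AE discontinuation near 4%, 8% and 12% and AE-driven reduction near 1%, 4.3% and 8%:

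| D | R | D/235 | (D + R)/235 | Share not in the discontinuation table, R/(D + R) |
|---|---|---|---|---|
| 9 | 2 | 3.8% | 4.7% | 18% |
| 9 | 10 | 3.8% | 8.1% | 53% |
| 9 | 19 | 3.8% | 11.9% | 68% |
| 19 | 2 | 8.1% | 8.9% | 10% |
| 19 | 10 | 8.1% | 12.3% | 34% |
| 19 | 19 | 8.1% | 16.2% | 50% |
| 28 | 2 | 11.9% | 12.8% | 7% |
| 28 | 10 | 11.9% | 16.2% | 26% |
| 28 | 19 | 11.9% | 20.0% | 40% |

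The gap therefore runs from 2/235 = 0.9 to 19/235 = 8.1 percentage points. If every reduced patient later stops for an AE (O = R), it is zero. For scale, the 10 patients that must be exceeded in SAP 10.4 are 10/235 = 4.3% of the active arm.

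One qualification applies to every row. All patients take one tablet on Days 1–14, so an AE stop in that period counts in D but is not intolerance of 5.6 mg. The either-outcome column is therefore an upper reading of 5.6 mg intolerance unless the two periods are separated.

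**The case against.** The case for leaving the plan alone has substance.

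- **The events are reported.** A reader might infer that AEs leading to reduction drop out of the AE tables altogether. They do not. SAP 11.1 says of the incidence summaries by SOC and preferred term: "Such summaries will be displayed for all TEAEs, oral cavity TEAEs, TEAEs by maximum severity, TEAEs by strongest relationship to study drug and post-treatment AEs". It adds: "In the AE data listings, all AEs will be displayed". Nothing excludes an event because it led to a reduction. Only the link between event and reduction is missing.
- **The patients are counted.** Because Protocol 10.3 confines reductions to AEs, the count in SAP 9.1 should approximate AE-driven reduction, and a reader can set it beside the AE discontinuations. This stands, but the two counts cannot be combined without the overlap, and neither names the event.
- **No table calls these patients tolerant.** It is tempting to say that the plan counts a reduced patient as tolerating treatment. The discontinuation table claims only to show discontinuations, and SAP 11 does not rank it as the main tolerability measure. The fault lies in reading it alone.
- **A reduction is not a proven averted discontinuation.** Protocol 10.3 speaks of events that might lead to stopping. Some reduced patients might have continued on two tablets.
- **Reductions may be few.** Protocol 5.4 and SAP 10.4 expect this. It limits the size of the gap, but the events behind the reductions would still be unreported as such.
- **The tables could be produced later.** SAP 2 permits unplanned analyses that are labelled as post hoc. That is true, but a tolerability summary specified before unblinding carries more weight.

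**Conclusion.** The point holds as a gap in safety reporting. Dose reduction is provided in place of AE-related discontinuation, no planned table summarises TEAEs leading to it, and AE-limited intolerance of 5.6 mg cannot be read from any planned output. The discontinuation table read alone understates it by the number of patients who reduced for an AE and did not later stop for one.

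That number cannot be derived from the documents. The range of 0.9 to 8.1 percentage points rests on assumed rates with no overlap; full overlap makes it zero. No hypothesis test, estimand or efficacy endpoint is affected. The documents do not support a stronger reading, either that these AEs go unreported or that a simple sum of stops and reductions measures intolerance of 5.6 mg. The change is worth making because it is cheap and bears directly on the secondary objective.

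**What to change.** In SAP 11.1 and 11.1.1, and in Protocol 13.5, add two summaries by arm, SOC and preferred term:

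1. TEAEs leading to dose reduction, whether temporary or lasting.
2. Patients with a TEAE leading to dose reduction or to discontinuation of study drug, each patient counted once.

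In the second, show events in the Day 1–14 one-tablet period separately from those after the increase to two tablets, so that only the latter are read as intolerance of 5.6 mg. Treat placebo tablet reductions in exactly the same way.

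For the link, use the action recorded for each AE (Protocol 12.3.1). The CRF itself is not available here. If that field has no dose-reduced option, use the dated reduction record, given that Protocol 10.2 requires reductions to be documented.

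This changes reporting only and leaves the dosing rules untouched. It costs SAP and protocol wording, two extra tables and possibly some work to match AE and dosing records. The tolerability figure may become slightly less favourable.
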